## 8 Safety and Adverse Events

### 8.1 Definitions

#### Unanticipated Problems Involving Risk to Subjects or Others (UPIRTSO)

Any unanticipated problem or adverse event that meets the following three criteria:

- Serious: Serious problems or events that results in significant harm, (which may be physical, psychological, financial, social, economic, or legal) or increased risk for the subject or others (including individuals who are not research subjects). These include: (1) death; (2) life threatening adverse experience; (3) hospitalization - inpatient, new, or prolonged; (4) disability/incapacity - persistent or significant; (5) birth defect/anomaly; (6) breach of confidentiality and (7) other problems, events, or new information (i.e. publications, DSMB reports, interim findings, product labeling change) that in the opinion of the local investigator may adversely affect the rights, safety, or welfare of the subjects or others, or substantially compromise the research data, **AND**
- Unanticipated: (i.e. unexpected) problems or events are those that are not already described as potential risks in the protocol, consent document, not listed in the Investigator's Brochure, or not part of an underlying disease. A problem or event is "unanticipated" when it was unforeseeable at the time of its occurrence. A problem or event is "unanticipated" when it occurs at an increased frequency or at an increased severity than expected, **AND**
- Related: A problem or event is "related" if it is possibly related to the research procedures.

### Drug Interactions

No drug interaction studies with Pentam 300 have been conducted.

Because the nephrotoxic effects may be additive, the concomitant or sequential use of pentamidine isethionate and other nephrotoxic drugs such as aminoglycosides, amphotericin B, cisplatin, foscarnet, or vancomycin should be closely monitored and avoided, if possible.

## Adverse Event

An untoward or undesirable experience associated with the use of a medical product (i.e. drug, device, biologic) in a patient or research subject.

The safety evaluation of this topical drug product during the conduct of a clinical trial includes an assessment of systemic safety as well as evaluation of local safety. Evaluation of systemic safety addresses warnings, precautions, and adverse events from approved product labeling for pentamidine isethionate (e.g., laboratory studies including renal and hepatic function, hematology, blood glucose, and calcium; periodic cardiac monitoring with electrocardiogram [ECG], and assessment for neuropsychiatric adverse events [including confusion and hallucinations]. The evaluation of systemic safety will be conducted at baseline (Visit 1, pre-operative), during treatment (Visit 3, Week 2), and after treatment (Visit 4, Week 4) and extended follow-up (Visit 5, Month 3). The local safety evaluation includes an active assessment of local tolerability (e.g. erythema, edema, vesication, necrosis, ulceration etc.) using an acceptable scale called the local skin reaction (LSR) grading scale [30]. The LSR grading scale uses a 0-4 numerical rating, with clinical descriptor and representative photographic images for each rating. The scale provides the ability to rate each LSR category (erythema, flaking/scaling, crusting, swelling, vesication/postulation and erosion/ulceration) and generate a composite objective LSR score [30].

## Serious Adverse Events

Adverse events are classified as serious or non-serious. Serious problems/events can be well defined and include;

- death
- life threatening adverse experience
- hospitalization
- inpatient, new, or prolonged; disability/incapacity
- persistent or significant disability or incapacity
- birth defect/anomaly
- tissue necrosis

[figure not shown]
and/or per protocol may be problems/events that in the opinion of the sponsor-investigator may have adversely affected the rights, safety, or welfare of the subjects or others, or substantially compromised the research data.

All adverse events that do not meet any of the criteria for serious, should be regarded as **non-serious adverse events**.

## Non-serious Adverse Events

- skin ulcers
- erythema
- reaction at site of administration
- rash

Routine monitoring of safety evaluation includes an active assessment of local tolerability (e.g. erythema, edema, vesication, necrosis, ulceration etc.) using an acceptable scale called the local skin reaction (LSR) grading scale as outlined below [30].

Grade	0	1	2	3	4
Erythema					
	Not present	Slightly pink <50%	Pink or light red >50%	Red, restricted to treatment area	Red extending outside treatment area
Flaking/Scaling					
	Not present	Isolated scale, specific to lesions	Scale <50%	Scale >50%	Scaling extending outside treatment area
Crusting					
	Not present	Isolated crusting	Crusting <50%	Crusting >50%	Crusting extending outside treatment area
Swelling	Not present	Slight, lesion specific oedema	Palpable oedema extending beyond individual lesions	Confluent and/or visible oedema	Marked swelling extending outside treatment area
Vesiculation/ Pustulation					
	Not present	Vesicles only	Transudate or pustules, with or without vesicles <50%	Transudate or pustules, with or without vesicles >50%	Transudate or pustules, with or without vesicles extending outside treatment area
Erosion/ Ulceration					
	Not present	Lesion specific erosion	Erosion extending beyond individual lesions	Erosion >50%	Black eschar or ulceration

## Adverse Event Reporting Period

For this study, the study treatment follow-up period is defined as 3 months following the last administration of study treatment.

**Preexisting Condition**

A preexisting condition is one that is present at the start of the study. A preexisting condition is recorded as an adverse event if the frequency, intensity, or the character of the condition worsens during the study period.

**General Physical Examination Findings**

At screening, any clinically significant abnormality is recorded as a preexisting condition. At the end of the study, any new clinically significant findings/abnormalities that meet the definition of an adverse event is recorded and documented as an adverse event.

**Post-study Adverse Event**

All unresolved adverse events are followed by the sponsor-investigator until the events have resolved, the subject is lost to follow-up, or the adverse event is otherwise explained. At the last scheduled visit, the sponsor-investigator instruct each subject to report, to the sponsor-investigator, any subsequent event(s) that the subject, or the subject's personal physician, believes might reasonably be related to participation in this study.

**Hospitalization, Prolonged Hospitalization or Surgery**

Any adverse event that results in hospitalization or prolonged hospitalization should be documented and reported as a serious adverse event unless specifically instructed otherwise in this protocol. Any condition responsible for surgery should be documented as an adverse event if the condition meets the criteria for an adverse event.

**8.2 Recording of Adverse Events**

At each contact with the subject, the study team must seek information on adverse events by specific questioning and, as appropriate, by examination. Information on all adverse events should be recorded immediately in the source document, and also in the appropriate adverse event section of the case report form (CRF). All clearly related signs, symptoms, and abnormal diagnostic, laboratory or procedure results should be recorded in the source document.

All adverse events occurring during the study period must be recorded. The clinical course of each event should be followed until resolution, stabilization, or until it has been ultimately determined that the study treatment or participation is not the probable cause. Serious adverse events that are still ongoing at the end of the study period must be followed up, to determine the final outcome. Any serious adverse event that occurs during the Adverse Event Reporting Period and is considered to be at least possibly related to the study treatment or study participation should be recorded and reported immediately.

**8.3 Reporting of Serious Adverse Events and Unanticipated Problems**

When an adverse event has been identified, the study team will take appropriate action necessary to protect the study participant and then complete the Study Adverse Event Worksheet and log. The sponsor-investigator will evaluate the event(s) and determine the necessary follow-up and reporting required.

### 8.3.1 Sponsor-Investigator reporting: notifying the Mayo IRB

The sponsor-investigator will report to the Mayo IRB any UPIRTSOs and Non-UPIRTSOs according to the Mayo IRB Policy and Procedures.

According to Mayo IRB Policy any serious adverse event (SAE) which the Principal Investigator has determined to be a UPIRTSO must be reported to the Mayo IRB as soon as possible but no later than 5 working days after the investigator first learns of the problem/event.

Information collected on the adverse event worksheet (and entered in the research database):

- Subject's name:
- Medical record number:
- Disease/histology (if applicable):
- The date the adverse event occurred:
- Description of the adverse event:
- Relationship of the adverse event to the research (drug, procedure, or intervention\*):
- If the adverse event was expected:
- The severity of the adverse event: (use a table to define severity scale 1-5\*\*)
- If any intervention was necessary:
- Resolution: (was the incident resolved spontaneously, or after discontinuing treatment)
- Date of Resolution:

All adverse events will be recorded in the Case Report Form. The sponsor-investigator will review all adverse events to determine if reports need to be made to the IRB and FDA. The sponsor-investigator will sign off on any adverse events that are reported in the Case Report Form within 24 hours. For this protocol, only directly related SAEs/UPIRTSOs will be reported to the IRB.

We will use of a table to define Relationship of an Event to the Research and to define the severity of each event.

#### \* Relationship Index

The relationship of an AE to the Investigational Drug is a clinical decision by the sponsor-investigator (PI) based on all available information at the time of the completion of the CRF and is graded as follows:

1. Not related: a reaction for which sufficient information exists to indicate that the etiology is unrelated to the study drug; the subject did not receive the study medication or the temporal sequence of the AE onset relative to administration of the study medication is not reasonable or the event is clearly related to other factors such as the subject's clinical state, therapeutic intervention or concomitant therapy.
2. Unlikely: a clinical event, including laboratory test abnormality, with a temporal relationship to drug administration which makes a causal relationship improbable and in which other drugs, chemicals, or underlying disease provide plausible explanations.

3. Possible: a clinical event, including laboratory test abnormality, with a reasonable time sequence to administration of the drug but which could also be explained by concurrent disease or other drugs or chemicals; information on drug withdrawals may be lacking are unclear.

4. Probable: a clinical event including laboratory test abnormality, with a reasonable time sequence to administration of the drug, unlikely to be attributed to concurrent disease or other drugs or chemicals and which follows a clinically reasonable response on withdrawal (de-challenge): re-challenge information is not required to fulfill this definition.

5. Definite: a reaction that follows a reasonable temporal sequence from administration of the drug, or in which the drug level has been established in body fluids or tissues, that follows a known or expected response pattern to the suspected drug, and that is confirmed by improvement on stopping or reducing the dosage of the drug, and reappearance of the reaction on repeated exposure (re-challenge).

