**Study Summary**

Title	Double Blind, Single-Center, Randomized, Within-Subject Placebo, Phase I Study Evaluating the Effects of Topical Pentamidine in Prevention of Hypertrophic Scar Formation
Running Title	Novel Topical Gel for Hypertrophic Scar Prevention
IRB Protocol Number	17-005230
Phase	Pilot Study
Methodology	Double Blind, Single-Center, Randomized, Within-Subject Placebo Phase I Study
Overall Study Duration	3 months
Subject Participation Duration	3 months
Single or Multi-Site	Single site
Objectives	Evaluate safety of topical pentamidine (TP) as an adjuvant to surgical scar excision (SSE) in the treatment of hypertrophic scar formation. Safety will be measured by serial monitoring for adverse events following the procedure and during treatment duration. Secondarily, study will evaluate drug quality and standardizations as well as investigate initial signs of efficacy.
Number of Subjects	10
Diagnosis and Main Inclusion Criteria	Hypertrophic scar diagnosed in Mayo Clinic Department of Dermatology or Division of Plastic Surgery, Rochester, Minnesota.
Study Product, Dose, Route, Regimen	Pentamidine, delivered as topical formulation containing 2% TP in silicone-containing base, PCCA Pracasil™-Plus (PP), versus placebo base alone. Approximately 1.8 mL of product in allotted single dose containers will be applied every 48 hours for 4 weeks following surgical scar excision.
Duration of Administration	Once every 48 hours for 4 weeks.
Reference therapy	SSE with silicone compounding base only (PCCA PP).
Statistical Methodology	The primary analysis will use descriptive statistics to document adverse events between treated and untreated lesions. The secondary analysis will use paired t-test or Wilcoxon signed rank test to compare the change in lesion height and characteristics between the treated and placebo groups following SSE (TP + PCCA PP vs. PCCA PP alone). In addition, two-factor analysis of variance (ANOVA) with repeated measures on both factors will be used to evaluate the effect of treatment and follow-up time for other continuous measures such as Vancouver Scar Scale (VSS) and Patient and Observer Scar Assessment Scale (POSAS).

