### 3.4 Primary Study Endpoints

**Aim #1:** Identify the type and number of serious adverse events related to TP in PCCA PP compared to PCCA PP base alone following surgical scar excision. While we do not anticipate any severe adverse events, we will monitor for the following:

- Skin infection
- Skin irritation
- Wound dehiscence
- Clinically significant abnormalities in physical examination and vital signs.

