#### **8.3.2 Sponsor-Investigator reporting: Notifying the FDA**

The sponsor-investigator will report to the FDA all serious, unexpected and suspected adverse reactions according to the required IND Safety Reporting timelines, formats and requirements.

Unexpected fatal or life threatening suspected adverse reactions where there is evidence to suggest a causal relationship between the study drug/placebo and the adverse event, will be reported as a serious suspected adverse reaction. This will be reported to the FDA on FDA Form 3500A, no later than 7 calendar days after the sponsor-investigator's initial receipt of the information about the event.

Other unexpected serious suspected adverse reactions where there is evidence to suggest a causal relationship between the study drug/placebo and the adverse event, will be reported as a serious suspected adverse reaction. This will be reported to the FDA on FDA Form 3500A, no later than 15 calendar days after the sponsor-investigator's initial receipt of the information about the event.

Any clinically important increase in the rate of serious suspected adverse reactions over those listed in the protocol or product insert will be reported as a serious suspected adverse reaction.

This will be reported to the FDA on FDA Form 3500A no later than 15 calendar days after the sponsor-investigator's initial receipt of the information about the event.

Findings from other studies in human or animals that suggest a significant risk in humans exposed to the drug will be reported. This will be reported to the FDA on FDA Form 3500A, no later than 15 calendar days after the sponsor-investigators initial receipt of the information about the event.

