#### **8.4 Unmasking/Unblinding Procedures**

The study statistician will be responsible for revealing the treatment assignments (i.e. unblinding) when necessary. Since no interim analysis is planned for this study, unblinding will occur only when 1) a serious adverse event is observed and the treatment assignment must be made known and/or 2) at the conclusion of the study at the time of data analysis to evaluate treatment safety and preliminary efficacy.

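### Aim #1 counts only serious events judged related, and that judgement may be made with the allocation known; comparing all events located to each scar end avoids this

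*Combined protocol and SAP*

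**What the plan says.** Section 3.4 gives Aim #1, the primary endpoint, as: "Identify the type and number of serious adverse events related to TP in PCCA PP compared to PCCA PP base alone". An event must be judged related before it enters this comparison. The Study Summary words the primary analysis differently: "The primary analysis will use descriptive statistics to document adverse events between treated and untreated lesions". That sentence has no relatedness filter and no restriction to serious events. I read its untreated lesion as the base-treated end, since each patient has TP at one end of the scar and base at the other.

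The tool for judging relatedness is the five-level Relationship Index in Section 8.3.1: "The relationship of an AE to the Investigational Drug is a clinical decision by the sponsor-investigator (PI) based on all available information". The grade is made "based on all available information at the time of the completion of the CRF". For reporting to the FDA, Section 8.3.2 uses a wider reference: "evidence to suggest a causal relationship between the study drug/placebo and the adverse event".

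Section 8.4 makes the study statistician responsible for revealing assignments. Before the end of the study, the only ground is that "a serious adverse event is observed and the treatment assignment must be made known".

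**The concern.** Relatedness decides which events count in the primary comparison between ends, so it should be judged in the same way at both ends. As written, it may not be. The kind of event that Aim #1 counts is also the kind that can lead to the code being opened. If the sponsor-investigator learns the allocation before completing the case report form (CRF), it becomes part of the information on which the grade rests.

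The Index asks about the drug. A grader who knows that an event arose at the base end has a reason to lower the grade, because no pentamidine was applied there, and to keep the grade for the same event at the TP end. A grader inclined towards the product could do the opposite. Either way, part of the difference between ends would come from opinions formed with the allocation known. One code break reveals both ends of that patient, so it can also bear on the grading of later events in the same patient.

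**Working it through.** **Reading the sections together**

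1. *Is relatedness a filter on the primary comparison?* Under Section 3.4 it is; under the Study Summary it is not. Section 7.2 names a paired t-test for the primary hypothesis but no variable, so it does not settle the matter.
2. *Can the grade be made with the allocation known?* Nothing requires the grade to be recorded before the code is opened, to be made by a masked assessor, or to be kept afterwards. Section 5.6 keeps investigators masked until after the analysis but does not address the exception in Section 8.4. Immediate recording (Section 8.2) and sign-off within 24 hours (Section 8.3.1) set no order relative to a code break.
3. *Does the wording treat the ends alike?* The Index grades against the investigational drug, and its top grade refers to drug levels and to the suspected drug's known response pattern. On the other hand, the worksheet item that it serves also covers procedure and intervention, and Section 5.2 and note g of the schedule in Section 6.11 use study drug for both gels. A masked grader can therefore apply the Index equally to both ends; the difference arises once the allocation is known.
4. *Which events are exposed?* Only those located to one end. For a systemic event, opening the code shows which end had TP, but the patient was already known to be receiving pentamidine.

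**Illustration of size**

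The plan states no adverse-event rate, so there is no figure of its own to reproduce here. The power statement in Section 7.1 (80% at 1.3 SD; 0.785 by an exact unpaired t calculation with 10 per group) does not enter.

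Inputs: 10 subjects (Section 3.2). Two assumptions: the same true risk p of a located serious event at each end, and a share u of base-end events graded away after a code break, with none graded away at the TP end.

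- Expected related count, TP end: 10p
- Expected related count, base end: 10p(1 − u)
- Ratio of expected counts: 10p / [10p(1 − u)] = 1/(1 − u)

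This gives 1/0.90 = 1.11 at u = 10%, 1/0.75 = 1.33 at 25%, and 1/0.50 = 2.00 at 50%.

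With counts this small, the chance that one end simply shows more events is also informative. Take p = 0.10 and independent ends, so the TP count is Binomial(10, 0.10) and the base count is Binomial(10, 0.10(1 − u)):

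| u | Expected TP | Expected base | P(TP > base) | P(TP < base) |
|---|---|---|---|---|
| 0 | 1.0 | 1.00 | 0.344 | 0.344 |
| 0.25 | 1.0 | 0.75 | 0.407 | 0.261 |
| 0.50 | 1.0 | 0.50 | 0.479 | 0.176 |
| 1 | 1.0 | 0 | 0.651 | 0 |

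The last row can be checked by hand: 1 − 0.9^10 = 0.651. At u = 0.50, P(TP > base) rises from 0.268 to 0.329 if p = 0.05, and from 0.388 to 0.623 if p = 0.20. If TP-end events were the ones discounted, the two columns would swap.

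**The case against.** The strongest reply is that several things must coincide before any harm is done. The code break needs a serious event and also a need to know the assignment. Section 8.4 does not say that the grader is told, and Section 5.6 points the other way. Section 3.4 anticipates no severe events. The lower grades of the Index can be applied to the base. The Study Summary already plans a description by lesion without the filter. All of this stands, and it makes the problem a possibility in a small number of events. It does not remove the gap, because no section fixes the order of grading and unmasking, and Section 3.4 still states the filtered comparison as the primary endpoint.

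A reader might infer more than the documents support:

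- *That every primary-endpoint event is exposed.* Each one meets only the first half of the condition in Section 8.4; the share meeting both halves is unknown. Events not located to one end are outside the mechanism.
- *That a base-end event can be called not related because* "the subject did not receive the study medication". That ground is worded per subject, and every dosed subject received pentamidine.
- *That follow-up of a base-end serious event may be cut short.* Section 8.2 does let follow-up run "until it has been ultimately determined that the study treatment or participation is not the probable cause", but the same paragraph requires serious events still open at study end to be followed to their outcome.
- *That the bias must run against TP.* It could run either way.

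**Conclusion.** The concern holds in a limited form. Sections 3.4 and the Study Summary disagree on whether the primary safety comparison is filtered by relatedness. Under the Section 3.4 version, events located to one scar end can be graded with the allocation known and so counted unequally. The bias is possible, not certain, and few events are at risk, perhaps none. With 10 subjects, however, one reclassified event can change the comparison.

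The ratios and probabilities above illustrate the mechanism and are not estimates. They rest on an assumed u, an assumed p, equal true risk, and independence between ends; the documents give none of these. What does not depend on assumptions is that a count of all located events would be free of this route to bias. I rate this a cheap improvement.

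**What to change.** - **Section 3.4 and Study Summary:** make the two agree. Define the between-end comparison as the count of all serious adverse events, and of all adverse events, located to each end regardless of relatedness. Keep the related-only count as supportive.
- **Systemic events:** report them per subject, outside the between-end comparison.
- **Section 8.3.1:** for located events, grade relatedness against the product applied at that end (A or B). Record on the CRF whether the grade came before or after any code break, and keep any grade made before it. The accrual-suspension criterion in Section 8.5 also uses the relatedness grade, so the sponsor should check that the two sections still read consistently; I propose no change to that criterion.

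None of this restricts or delays a code break. The cost is a wording change in these places and one CRF field, plus a scar-end item if the form lacks one, since the worksheet list in Section 8.3.1 shows none. No further patients, visits or staff are needed. The downside is that the all-event count includes surgical complications at both ends, which adds background events and can dilute a true difference. The supportive related-only count partly answers that.
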